4.4.6 Other Safety Analyses

The results of eC-SSRS assessments will be listed for each subject. The incidence of treatment-emergent suicidal ideation or suicidal behavior will be summarized by modal dose group and visit using descriptive statistics as appropriate.

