4.4.4 Vital Signs

Descriptive statistics for vital signs parameters (ie, diastolic and systolic BP, pulse, respiration rate, temperature) and weight, and changes from Baseline will be presented by visit and treatment group.

Vital sign values will be listed. Clinically notable vital sign values will be identified on the listings as those above (H) or below (L) a clinically notable range ([Table 1](#)). Categorical analyses of subjects (number and percent) who fall outside the below clinically notable vital sign ranges will also be presented by modal dose group and visit.

Table 1 Vital Sign and Weight

Variable	Criterion value ^a	Change relative to baseline ^a	Clinically notable range
Heart rate	>120 bpm	Increase of ≥ 15 bpm	H
	<50 bpm	Decrease of ≥ 15 bpm	L
Systolic BP	>180 mmHg	Increase of ≥ 20 mmHg	H
	<90 mmHg	Decrease of ≥ 20 mmHg	L
Diastolic BP	>105 mmHg	Increase of ≥ 15 mmHg	H
	<50 mmHg	Decrease of ≥ 15 mmHg	L

BP = blood pressure, bpm = beats per minute, H = high, L = low.

Clinically notable means that a value must meet the criterion value and must attain the specified magnitude of change relative to baseline.

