4.4.5 Electrocardiograms

Descriptive statistics for ECG parameters and changes from Baseline will be presented by modal dose group. Shift tables will present changes from Baseline in ECG interpretation (categorized as normal; abnormal, not clinically significant; and abnormal, clinically significant) by visit. Later on, shift tables may be presented by post baseline year instead of visit as deemed appropriate.

For each subject, the maximum observed corrected QT interval calculated using Fridericia's formula (QTcF), and the maximum prolongation from baseline in QTcF will be compiled. Categorical analyses of subjects (number and percent) with maximum observed QTcF values >450 msec, >480 msec, and >500 msec and maximum prolongations (from Baseline) in QTcF >30 msec and >60 msec will be presented by modal dose group and by time point. Categorical analyses of subjects (number and percent) with maximum observed PR values >220 msec, and QRS values > 120 msec will be presented by modal dose group and by visit.

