7.1.4 Visit Window

All efficacy and safety data will be presented using derived visits as follows.

Visit	Target Visit Day (in study days)	Visit Window (in study days)
Ext. Visit 6B		On or prior to the study day of first dose of Extension Phase
Ext. Visit 7	73	Post study day of first dose of Extension Phase - 88
Ext. Visit 8	103	89-118
Ext. Visit 9	133	119-148
Ext. Visit 10	163	149-178
Ext. Visit 11	193	179-208
Ext. Visit 12	223	209-238
Ext. Visit 13	253	239-268
Ext. Visit 14	283	269-298
Ext. Visit 15	313	299-328
..etc	X	(X -14, X+15)

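### Suicidality and notable vital signs are summarized only by visit, so no planned table gives the number of subjects ever affected, and the scope of the ECG maxima is unclear

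*SAP*

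**What the plan says.** The only objective in SAP Section 2.1 is safety and tolerability over 30 months of flexible dosing. The relevant tabulation rules are these.

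- **Suicidality (Section 4.4.6).** "The results of eC-SSRS assessments will be listed for each subject". The summary rule is: "The incidence of treatment-emergent suicidal ideation or suicidal behavior will be summarized by modal dose group and visit", with descriptive statistics as appropriate.
- **Notable vital signs (Section 4.4.4).** Values are flagged high or low on the listings. Subjects "who fall outside the below clinically notable vital sign ranges will also be presented by modal dose group and visit".
- **PR and QRS (Section 4.4.5).** The categorical analysis is of subjects "with maximum observed PR values >220 msec, and QRS values > 120 msec will be presented by modal dose group and by visit".
- **QTcF (Section 4.4.5).** One maximum value and one maximum prolongation are compiled per subject. The threshold counts are then shown by modal dose group and time point.
- **Visits (Section 7.1.4).** "All efficacy and safety data will be presented using derived visits as follows". The windows are 30 days wide after the first one. Section 8 repeats the instruction.

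Two other sections use a different unit. Section 4.4.2 counts a subject once within a system organ class and preferred term, however many events occur. Section 4.4.3 counts a subject once per laboratory parameter and direction for markedly abnormal values.

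**The concern.** Section 4.4.6 promises an incidence. Over a long extension, that means the number of subjects who had the event at any time, divided by the number at risk. A by-visit table gives something else: the proportion of those assessed in a window who were positive in that window. Infrequent, intermittent findings then appear as isolated ones and twos across many rows, and the rows do not show whether these are the same people.

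How many subjects ever had suicidal ideation or behavior, or a notable vital sign, is a basic question for an open-label safety extension. Section 5 says interim outputs will support new drug applications, so the answer should come from a planned table with a stated counting rule.

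The ECG wording raises a related problem. A subject's maximum over follow-up is one number and belongs to no particular row of a by-visit table. Two programmers could reasonably build different tables from the same sentence.

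**Working it through.** The SAP states no figure for this point, so there is nothing to reproduce. The check has three steps.

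**1. What by-visit counts determine.** A subject has one modal dose, so stays in one column of a given analysis. Let a column hold k positive subject-visits, each subject counted at most once per row. The number of distinct subjects affected is at least the largest count in any single row, and at most the smaller of k and the column size. When no row holds more than one positive, the range is 1 to k. Nothing else in the table narrows it.

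**2. How many rows there could be.** Inputs are the window rule in Section 7.1.4 (first window ends at study day 88, then 30 days each) and the 30-month maximum in Section 2.2.2. The first Extension dose is assumed near study day 43, that is, 73 − 30.

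- Rule X − 14 to X + 15 for targets 103, 133, …, 313 gives 89–118, 119–148, …, 299–328, which matches every printed window from Visit 8 to Visit 15.
- Number of windows = 1 + ceil((last day − 88)/30).
- With 30 months taken as 900 days: last day = 43 + 900 = 943, so 1 + ceil(855/30) = 1 + 29 = 30.
- With 913 days: last day = 956, so 1 + ceil(868/30) = 1 + 29 = 30.
- With the first dose 30 days later (day 73) and 900 days: 1 + ceil(885/30) = 1 + 30 = 31.

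There are thus about 30 derived windows. This is an upper bound on rows with data: Section 2.2.1 allows telephone visits, the note to Figure 1 says some subjects will have fewer visits, and the assessment schedule is not in the SAP.

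**3. Illustration of the range.** The SAP gives no event rates. Assume 60 subjects, all attending, with exactly one positive per assessed visit (1/60 = 1.7% in each row). Sixty is the approximate Core Study enrollment in Section 3. The Extension can be no larger, and its columns are split by modal dose, so real denominators will be smaller. For k assessed visits:

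- same subject every time: 1 subject
- independent visits: 60 × [1 − (1 − 1/60)^k]
- a different subject every time: k subjects

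| Assessed visits k | Fewest ever affected | If visits independent | Most ever affected |
|---|---|---|---|
| 6 | 1 (1.7%) | 5.8 (9.6%) | 6 (10%) |
| 10 | 1 (1.7%) | 9.3 (15.5%) | 10 (16.7%) |
| 30 | 1 (1.7%) | 23.8 (39.6%) | 30 (50%) |

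Every case in a given row of this table produces the same by-visit output. The ambiguity does not depend on there being 30 assessments; it is present with 6.

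**ECG wording.** For QTcF, Section 4.4.5 explicitly compiles a maximum per subject and then splits it by time point. For PR and QRS it refers to the maximum observed value and splits it by visit. The phrase fits a by-visit table only if it means the largest of several readings within a window. The SAP does not say that this is meant.

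**The case against.** The strongest reply is that no information is lost. eC-SSRS results are listed by subject, notable vital signs are flagged on listings, and Section 7.1.3 lists individual data. With at most about 60 subjects, a hand count is feasible. This stands: a reader might infer that the plan can never yield the number of subjects affected, and the documents do not support that. What is missing is a planned summary. A hand count has no stated rule for the worst value or for unscheduled visits, and Section 2.2.1 expects unscheduled visits to occur.

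It can also be said that the phrase about descriptive statistics as appropriate leaves room for an overall row, and that table layouts are in separate shells (Section 10). Both are true. But permission is not a requirement, and shells should implement the unit the SAP states, which here is the visit.

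Three further readings go too far.

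- A reader might take PR and QRS to be counted visit by visit only. The wording about a maximum points to one value per subject, so the fault is inconsistency, and QTcF shares it.
- A reader might infer that shrinking denominators make by-visit percentages too low. They can do the opposite: one event among 5 remaining subjects is 20%, against 1/20 = 5% ever affected in a group of 20. Understatement arises when events are spread over different subjects and visits, so the direction of error is not fixed.
- A reader might assume some 30 assessments per subject, or a large gap between the two measures. The SAP supports neither.

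The analysis is descriptive with no hypothesis tests (Section 4), so no inference is at risk.

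**Conclusion.** The point holds for suicidality and notable vital signs. The only summary specified for each is by modal dose group and visit. That does not give the incidence over the Extension, and it departs from the once-per-subject counting the SAP uses for adverse events and markedly abnormal laboratory values, with no reason stated. For PR, QRS and QTcF the finding is narrower: the scope of the maximum is unclear, and the text is inconsistent if it means the maximum over follow-up.

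The size is not known. The logical range is 1 to k subjects for k positives at k different visits, with k limited by an assessment schedule outside the SAP. The figures in the working rest on an assumed 60 subjects, full attendance and one positive per visit, and are not a forecast. Because safety is the sole objective, the change should be made before the tables are programmed. It is a defect of summary, not a threat to the data.

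**What to change.** 1. In Sections 4.4.4 and 4.4.6, add a row for any time post-baseline in the Extension Phase. Count each subject once, include unscheduled visits, and present it by modal dose and in total. State the denominator, for example subjects with at least one post-baseline assessment of that measure.
2. In Section 4.4.5, for PR, QRS and QTcF (including QTcF prolongation), use the subject's maximum over the Extension in an any-time row and the observed value in the by-visit rows.
3. Keep the by-visit rows as supportive.
4. In Sections 7.1.4 and 8, say that any-time rows draw on all post-baseline Extension records and are not tied to a derived visit.

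The cost is a few sentences in the SAP and one extra row per table, with matching edits to the shells. No new data are needed.

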5 INTERIM ANALYSES

Interim analyses will be performed for this study to provide data for a synoptic report to support new drug applications.

6 CHANGES IN THE PLANNED ANALYSES

No efficacy analysis set has been defined for extension phase and safety set will be used for all analysis.

7 DATA ANALYSIS GENERAL CONSIDERATIONS

The Safety Set will be used for all analyses.

7.1.1 Examination of Subgroups

No subgroup analysis is planned for this Extension Phase.

7.1.2 Handling of Missing Data, Dropouts, and Outliers

Data will not be imputed, unless otherwise specified; i.e., all missing values will remain as missing in all statistical summaries and listings, unless otherwise specified.

Outliers: No formal statistical analyses will be performed to detect and/or remedy the presence of statistical outliers.

7.1.3 Other Considerations

Individual subject data in the database will be presented in data listings.

7.1.4 Visit Window

All efficacy and safety data will be presented using derived visits as follows.

Visit	Target Visit Day (in study days)	Visit Window (in study days)
Ext. Visit 6B		On or prior to the study day of first dose of Extension Phase
Ext. Visit 7	73	Post study day of first dose of Extension Phase - 88
Ext. Visit 8	103	89-118
Ext. Visit 9	133	119-148
Ext. Visit 10	163	149-178
Ext. Visit 11	193	179-208
Ext. Visit 12	223	209-238
Ext. Visit 13	253	239-268
Ext. Visit 14	283	269-298
Ext. Visit 15	313	299-328
..etc	X	(X -14, X+15)

8 PROGRAMMING SPECIFICATIONS

All efficacy and safety data will be presented using derived visit window described in this SAP. The rules for programming derivations and dataset specifications are provided in separate documents.

9 STATISTICAL SOFTWARE

All statistical analyses will be performed using SAS v 9.3 or later.

10 MOCK TABLES, LISTINGS, AND GRAPHS

The study table, listing, and graph (TLG) shells will be provided in a separate document, which will show the content and format of all tables, listings, and graphs in detail.

12 APPENDICES

Appendix 12.1 Sponsor's Grading for Determining Markedly Abnormal Laboratory Results

The following table of Sponsor's Grading for Laboratory Values is taken from the protocol.

Sponsor's Grading for Laboratory Values

	Grade 1	Grade 2	Grade 3	Grade 4
BLOOD/BONE MARROW				
Hemoglobin	<LLN – 10.0 g/dL <LLN – 100 g/L <LLN – 6.2 mmol/L	<10.0 – 8.0 g/dL <100 – 80 g/L <6.2 – 4.9 mmol/L	<8.0 g/dL <80 g/L <4.9 mmol/L; transfusion indicated	life-threatening consequences; urgent intervention indicated
Leukocytes (total WBC)	<LLN – 3.0×10^9 /L <LLN – 3000/mm ³	<3.0 – 2.0×10^9 /L <3000 – 2000/mm ³	<2.0 – 1.0×10^9 /L <2000 – 1000/mm ³	<1.0 $\times 10^9$ /L <1000/mm ³
Lymphocytes	<LLN – 800/mm ³ <LLN – 0.8×10^9 /L	<800 – 500/mm ³ <0.8 – 0.5×10^9 /L	<500 – 200/mm ³ <0.5 – 0.2×10^9 /L	<200/mm ³ <0.2 $\times 10^9$ /L
Neutrophils	<LLN – 1.5×10^9 /L <LLN – 1500/mm ³	<1.5 – 1.0×10^9 /L <1500 – 1000/mm ³	<1.0 – 0.5×10^9 /L <1000 – 500/mm ³	<0.5 $\times 10^9$ /L <500/mm ³
Platelets	<LLN – 75.0×10^9 /L <LLN – 75,000/mm ³	<75.0 – 50.0×10^9 /L <75,000 – 50,000/mm ³	<50.0 – 25.0×10^9 /L <50,000 – 25,000/mm ³	<25.0 $\times 10^9$ /L <25,000/mm ³
METABOLIC/LABORATORY				
Albumin, serum- low (hypoalbuminemia)	<LLN – 3 g/dL <LLN – 30 g/L	<3 – 2 g/dL <30 – 20 g/L	<2 g/dL <20 g/L	life-threatening consequences; urgent intervention indicated
Alkaline phosphatase	>ULN – $3.0 \times$ ULN	>3.0 – $5.0 \times$ ULN	>5.0 – $20.0 \times$ ULN	>20.0 \times ULN
ALT	>ULN – $3.0 \times$ ULN	>3.0 – $5.0 \times$ ULN	>5.0 – $20.0 \times$ ULN	>20.0 \times ULN
AST	>ULN – $3.0 \times$ ULN	>3.0 – $5.0 \times$ ULN	>5.0 – $20.0 \times$ ULN	>20.0 \times ULN
Bilirubin (hyperbilirubinemia)	>ULN – $1.5 \times$ ULN	>1.5 – $3.0 \times$ ULN	>3.0 – $10.0 \times$ ULN	>10.0 \times ULN
Calcium, serum-low (hypocalcemia)	<LLN – 8.0 mg/dL <LLN – 2.0 mmol/L	<8.0 – 7.0 mg/dL <2.0 – 1.75 mmol/L	<7.0 – 6.0 mg/dL <1.75 – 1.5 mmol/L	<6.0 mg/dL <1.5 mmol/L
Calcium, serum-high (hypercalcemia)	>ULN – 11.5 mg/dL >ULN – 2.9 mmol/L	>11.5 – 12.5 mg/dL >2.9 – 3.1 mmol/L	>12.5 – 13.5 mg/dL >3.1 – 3.4 mmol/L	>13.5 mg/dL >3.4 mmol/L
Cholesterol, serum-high (hypercholesterolemia)	>ULN – 300 mg/dL >ULN – 7.75 mmol/L	>300 – 400 mg/dL >7.75 – 10.34 mmol/L	>400 – 500 mg/dL >10.34 – 12.92 mmol/L	>500 mg/dL >12.92 mmol/L
Creatinine	>ULN – $1.5 \times$ ULN	>1.5 – $3.0 \times$ ULN	>3.0 – $6.0 \times$ ULN	>6.0 \times ULN
GGT (γ -glutamyl transpeptidase)	>ULN – $3.0 \times$ ULN	>3.0 – $5.0 \times$ ULN	>5.0 – $20.0 \times$ ULN	>20.0 \times ULN
Glucose, serum-high (hyperglycemia)	Fasting glucose value: >ULN – 160 mg/dL >ULN – 8.9 mmol/L	Fasting glucose value: >160 – 250 mg/dL >8.9 – 13.9 mmol/L	>250 – 500 mg/dL; >13.9 – 27.8 mmol/L; hospitalization indicated	>500 mg/dL; >27.8 mmol/L; life-threatening consequences
Glucose, serum-low (hypoglycemia)	<LLN – 55 mg/dL	<55 – 40 mg/dL	<40 – 30 mg/dL	<30 mg/dL

Sponsor's Grading for Laboratory Values

	Grade 1	Grade 2	Grade 3	Grade 4
	<LLN – 3.0 mmol/L	<3.0 – 2.2 mmol/L	<2.2 – 1.7 mmol/L	<1.7 mmol/L life-threatening consequences; seizures
Phosphate, serum-low (hypophosphatemia)	<LLN – 2.5 mg/dL <LLN – 0.8 mmol/L	<2.5 – 2.0 mg/dL <0.8 – 0.6 mmol/L	<2.0 – 1.0 mg/dL <0.6 – 0.3 mmol/L	<1.0 mg/dL <0.3 mmol/L life-threatening consequences
Potassium, serum-high (hyperkalemia)	>ULN – 5.5 mmol/L	>5.5 – 6.0 mmol/L	>6.0 – 7.0 mmol/L hospitalization indicated	>7.0 mmol/L life-threatening consequences
Potassium, serum-low (hypokalemia)	<LLN – 3.0 mmol/L	<LLN – 3.0 mmol/L; symptomatic; intervention indicated	<3.0 – 2.5 mmol/L hospitalization indicated	<2.5 mmol/L life-threatening consequences
Sodium, serum-high (hypernatremia)	>ULN – 150 mmol/L	>150 – 155 mmol/L	>155 – 160 mmol/L hospitalization indicated	>160 mmol/L life-threatening consequences
Sodium, serum-low (hyponatremia)	<LLN – 130 mmol/L	N/A	<130 – 120 mmol/L	<120 mmol/L life-threatening consequences
Triglyceride, serum-high (hypertriglyceridemia)	150 – 300 mg/dL 1.71 – 3.42 mmol/L	>300 – 500 mg/dL >3.42 – 5.7 mmol/L	>500 – 1000 mg/dL >5.7 – 11.4 mmol/L	>1000 mg/dL >11.4 mmol/L life-threatening consequences
Uric acid, serum-high (hyperuricemia)	>ULN – 10 mg/dL ≤0.59 mmol/L without physiologic consequences	N/A	>ULN – 10 mg/dL ≤0.59 mmol/L with physiologic consequences	>10 mg/dL >0.59 mmol/L life-threatening consequences

Based on Common Terminology Criteria for Adverse events (CTCAE) Version 4.0. Published: 28 May 2009 (v4.03: 14 Jun, 2010).

ALT = alanine aminotransferase (serum glutamic pyruvic transaminase), AST = aspartate aminotransferase (serum glutamic oxaloacetic transaminase), GGT = γ -glutamyl transpeptidase, , LLN = lower limit of normal, N/A = not applicable, ULN = upper limit of normal, WBC = white blood cell.

SIGNATURE PAGE

Author:

PPD

Date

Approval:

PPD

Date

PPD

Date
